12. MEASUREMENT OF EFFECT

Although the clinical benefit of these drugs has not yet been established, the intent of offering this treatment is to provide a possible therapeutic benefit, and thus the patient will be carefully monitored for tumor response and symptom relief in addition to safety and tolerability. Patients with measurable disease will be assessed by standard criteria. For the purposes of this study, patients should be re-evaluated at the end of every even cycle. Additional bone marrow procedures may also be obtained as clinically indicated following initial documentation of a CR.

12.1 Hematologic Tumors

Treatment responses will be classified according to the IWG revised criteria for response assessment in AML (Cheson *et al.*, 2003); the ELN recommendations for diagnosis and management of AML (Dohner *et al.*, 2010); and the IWG application and proposal for modification of response criteria in MDS (Cheson *et al.*, 2006).

Bone marrow blast percentages will be defined by manual differential count on the aspirate.

Morphologic complete remission (CR): <5% bone marrow blasts and no blasts with Auer rods with no requirement for bone marrow cellularity, as long as absolute neutrophil count (ANC) $\geq 1000/\text{mcL}$ AND platelets $\geq 100,000/\text{mcL}$, patient is transfusion-independent, and has no residual evidence of extramedullary leukemia. Persistent dysplasia is allowed.

Morphologic complete remission with incomplete blood count recovery (CRi): All criteria for morphologic CR must be met, except that the patient has residual neutropenia (ANC $< 1000/\text{mcL}$) or thrombocytopenia (platelets $< 100,000/\text{mcL}$).

Morphologic leukemia-free state (MLFS): <5% bone marrow blasts, no blasts with Auer rods, and no persistent extramedullary leukemia, peripheral blood count recovery not required.

Cytogenetic complete remission (CRc): There should be no evidence of a previously present cytogenetic abnormality (*e.g.*, t(8;21), inv 16, t(9;22), *etc.*) by conventional karyotyping or Fluorescent in situ hybridization (FISH) (must be specified).

Molecular complete remission (CRm): There should be no evidence of a previously present molecular abnormality (*e.g.*, BCR-ABL, mutated FLT3, NPM1, or CEBPA, *etc.*). The sensitivity of the PCR assay must be specified.

Partial remission (PR): All peripheral blood criteria for CR must be met, with a decrease of at least 50% in the percentage of blasts to 5% to 24% in the bone marrow aspirate. A value of <5% bone marrow blasts will be considered a PR if Auer rods are present.

Stable disease (SD): Patients not meeting criteria for CR, CRi, ML-FS, CRc, CRm, PR, relapse, or progressive disease.

Morphologic relapse: Relapse after CR is defined as reappearance of leukemic blasts in the

peripheral blood or $\geq 5\%$ blasts in the bone marrow not attributable to any other cause (*e.g.*, bone marrow regeneration). Relapse from PR is defined as $\geq 25\%$ bone marrow blasts not attributable to bone marrow regeneration or use of colony stimulating factors. The appearance of new dysplastic changes should also be considered relapse.

Progressive Disease: Any of the following in patients who have not previously met CR, CRi, CRc, CRm, ML-FS, or PR criteria while on study therapy:

- $\geq 50\%$ increase in the bone marrow blasts (by aspirate differential count) over the best previous assessment (comparing to a minimum bone marrow blast percentage threshold of 20% at baseline or during study at such time as that threshold is met).
- $\geq 50\%$ increase in peripheral blood absolute blast count over the best previous assessment (comparing to a minimum peripheral blood absolute blast count threshold of $\geq 1000/\text{mL}$ at baseline or during study at such time as that threshold is met). In some cases, the peripheral blood absolute blast count may not accurately reflect disease burden, especially with targeted therapies. At investigator discretion, the patient can continue on study with close monitoring of peripheral blood absolute blast count and bone marrow biopsies to assess bone marrow blast percentage (by aspirate differential count) as clinically indicated.
- Development of new extramedullary disease.

Appearance of new dysplastic changes should be closely monitored for emerging relapse. In a patient who has been recently treated, dysplasia or a transient increase in blasts may reflect a chemotherapy effect and recovery of hematopoiesis. Cytogenetics should be tested to distinguish true relapse from therapy-related MDS/AML.

Duration of remission is defined only for patients who achieve CR, CRi, CRc, or CRm and is measured by the interval from the date of CR (by blood count recovery and BM examination), until the date of relapse.

Cytogenetic responses: For patients with AML or MDS, a complete cytogenetic response requires the disappearance of a previously present cytogenetic abnormality (without appearance of new ones), while a partial cytogenetic response requires a $\geq 50\%$ reduction in the number of metaphases positive for the chromosomal abnormality by conventional karyotyping.

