9.3.3 Response-Evaluable Population

Response-evaluable patients are those who have received any doses of belinostat or MLN4924 (pevonedistat) and have had at least one post-treatment response evaluation. For response evaluation, the patients are coded as having a response or not having a response as follows:

- Responders - Those patients whose best response assessment is a CR, CRi, CRc, CRm, ML-FS, or PR.
- Non-Responders - Those patients whose best response assessment is SD, morphologic relapse, or progression, or those patients who were not assessed or who were not evaluable.

The coding of patients as responders or non-responders will be made by the PI with the concurrence of the biostatistician.

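### Section 12.1: as written, no response category requires leukemic blasts to be gone from the blood, although relapse after CR is defined by their return

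*Combined protocol and SAP*

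**What the plan says.** Section 12.1 begins: "Treatment responses will be classified according to the IWG revised criteria for response assessment in AML". It also names the ELN recommendations and an IWG paper on MDS. It then writes out its own definitions and does not say which text prevails if they differ.

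- **CR:** "<5% bone marrow blasts and no blasts with Auer rods with no requirement for bone marrow cellularity", plus neutrophil and platelet thresholds, and "patient is transfusion-independent, and has no residual evidence of extramedullary leukemia".
- **CRi:** "All criteria for morphologic CR must be met, except that the patient has residual neutropenia" or low platelets.
- **ML-FS:** "<5% bone marrow blasts, no blasts with Auer rods, and no persistent extramedullary leukemia, peripheral blood count recovery not required".
- **PR:** "All peripheral blood criteria for CR must be met", with marrow blasts at least halved to 5–24%, or below 5% if Auer rods are present.
- **CRc and CRm:** a cytogenetic or molecular abnormality seen before is no longer found.
- **Relapse:** "Relapse after CR is defined as reappearance of leukemic blasts in the" peripheral blood, or marrow blasts of at least 5%. From PR, the trigger is marrow blasts of at least 25%. New dysplastic changes also count.
- **Progressive Disease:** open only to patients who have not already met a response category on study. The triggers are a rise of at least 50% in marrow blasts, a rise of at least 50% in the blood blast count (each subject to a minimum level), or new extramedullary disease.

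Section 9.3.3 counts as responders "Those patients whose best response assessment is a CR, CRi, CRc, CRm, ML-FS, or PR".

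**The concern.** The relapse rule treats blasts in the blood as evidence of leukemia and assumes that remission cleared them. The response rules never ask whether they cleared, so the two halves of Section 12.1 do not fit together.

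The gap matters in this population. Exclusion 3.2.14 bars only circulating blast counts above 50,000, and the footnotes to the biomarker table in Section 5.1 make certain blood samples mandatory when at least 10% blasts are expected in the blood. Marrow percentages come from the aspirate differential. An aspirate that under-represents the disease can therefore produce a response category while the blood differential still shows leukemic blasts.

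At stake are the response rate and its 95% limits (Section 9.4.2) and the durations that start from a response.

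**Working it through.** The plan states no figure on this point, so there is none to reproduce. The check applies the written rules.

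**Step 1. Look for a blood-blast condition in each category.**

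| Category | Conditions as written | Blood blasts must be absent? |
|---|---|---|
| CR | marrow <5%, no Auer-rod blasts, ANC, platelets, transfusion independence, no extramedullary disease | not stated |
| CRi | as CR, counts relaxed | not stated |
| ML-FS | marrow <5%, no Auer-rod blasts, no extramedullary disease | not stated |
| PR | blood criteria of CR (counts and transfusion independence), marrow halved to 5–24% or <5% with Auer rods | not stated |
| CRc, CRm | abnormality no longer found | not stated |

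**Step 2. Enumerate the rules.** CR, CRi, ML-FS and PR were coded as logical rules. Inputs were marrow blasts of 2%, 10% or 30% (from an assumed baseline of 40%) and yes/no values for Auer rods, ANC, platelets, transfusion independence and extramedullary disease. That gives 3 × 2⁵ = 96 combinations, each classified with blood blasts absent and present. The category was the same in all 96 pairs. This follows from the table, because no written condition refers to blood blasts.

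**Step 3. Apply the relapse rule to blasts that never cleared.**

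- CR, literal reading: blasts that never left cannot reappear, so the blood trigger is unavailable. The marrow and dysplasia triggers remain.
- CRi and ML-FS: no relapse rule is written specifically for either.
- PR: blood blasts are not a relapse trigger.

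**Step 4. Apply the progression rule at a first response assessment.** Illustrative values: marrow falls from 30% to 4%, with no Auer rods and no extramedullary disease. Blood blasts rise from 2,000 to 3,000 in the section's units, above its threshold of 1,000.

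- ML-FS: 4% < 5% and the other conditions hold, so it is met.
- Progressive Disease: 3,000/2,000 − 1 = 50%, so the blood trigger is met. No response was met previously, so the patient is not excluded.

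Both categories apply on the same day.

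**Step 5. Size of one recoded patient.** The denominators are 45 (maximum sample size, Section 9.2) and 12 (expansion, Section 6.4).

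- 1/45 = 2.2 percentage points.
- 1/12 = 8.3 percentage points. For example, 3/12 = 25.0% (exact 95% limits 5.5–57.2%) becomes 2/12 = 16.7% (2.1–48.4%).

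**The case against.** **The cited criteria may supply the condition.** Section 12.1 says responses are classified by the IWG and ELN papers, and its own definitions may only summarize them. This limits the point to the written text, since the papers are not reproduced and cannot be checked here. It does not remove the point: the written definitions read as complete lists, and nothing says the papers override them.

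**Other conditions may cover it.** The Auer-rod condition is not restricted to marrow, so it may bar blood blasts that contain Auer rods from CR, CRi and ML-FS; blasts without them still pass. The ban on extramedullary leukemia does not clearly help, because the progression list treats blood blasts and extramedullary disease as separate items.

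**The endpoint is secondary.** The primary endpoint is the RP2D, found from the Section 6 criteria. All analyses are descriptive, and responders are coded by the principal investigator with the biostatistician's concurrence. This stands and limits the consequence to reporting of activity. Case-by-case judgement does not replace a stated rule.

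**Three stronger readings are tempting but unsupported.**

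- A reader might infer that patients can generally be in response and relapse on the same day. For PR this cannot happen through blood blasts, because PR needs marrow blasts below 25% and relapse from PR needs at least 25%. For CRi and ML-FS it requires extending the after-CR rule to them. For CR it requires reading reappearance as mere presence.
- A reader might infer a duration of zero for an ML-FS patient with persistent blood blasts. No written rule gives that: duration of response in Section 9.1 ends at progression or death, and duration of remission in Section 12.1 does not cover ML-FS.
- A reader might want the probability that at least one responder is affected. The documents give neither an expected response rate nor the share of responders with residual blood blasts, so any such figure would reflect only the guesses put in.

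**Conclusion.** The point holds for the definitions written in Section 12.1. A patient with persistent circulating leukemic blasts who meets the marrow and other conditions is coded a responder. For such a patient in CR, relapse cannot be called on blood findings if the rule is read literally. At a first response assessment, ML-FS and Progressive Disease can coincide, because only patients who responded previously are excluded from progression.

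The number affected is unknown. The 2.2 and 8.3 points are the effect of one patient, not an expected bias. The conclusion assumes that sites code from the written text; if the cited criteria require clear blood and are meant to prevail, the defect is that the protocol does not say so. RP2D selection by the Section 6 criteria is unaffected. The wording should still be corrected, because the present rule can misclassify and the repair is small.

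**What to change.** In Section 12.1:

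1. Add to CR and to ML-FS: no leukemic blasts in the peripheral blood, by the CBC differential at or nearest the disease assessment. CRi and PR then inherit it through their references to CR. The team should confirm that this tightening of PR is intended.
2. Apply the same condition to CRc and CRm, which do not inherit from CR.
3. State whether the written definitions or the cited IWG and ELN criteria prevail where they differ.
4. State which relapse rule applies to CRi and to ML-FS.

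The cost is a few sentences. CR already needs an ANC, and the study calendar includes a CBC with differential before Day 1 of subsequent cycles. Disease assessment falls at the end of every even cycle and the calendar does not tie a differential to the aspirate date, hence the words *at or nearest*. The reported response rate may be slightly lower.

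### ML-FS responders have no blast-based or extramedullary rule that ends response, and the fixed 25% threshold misses regrowth in PR patients who entered with 10% to under 25% marrow blasts

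*Combined protocol and SAP*

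**What the plan says.** Section 9.3.3 defines responders as "Those patients whose best response assessment is a CR, CRi, CRc, CRm, ML-FS, or PR".

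Section 12.1 then gives these ways to record loss of disease control:

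- **After CR.** "Relapse after CR is defined as reappearance of leukemic blasts in the" peripheral blood, or at least 5% marrow blasts with no other cause.
- **From PR.** "Relapse from PR is defined as" at least 25% marrow blasts, except where regeneration or growth factors explain them. Neither entry level nor nadir is mentioned.
- **New dysplasia.** "The appearance of new dysplastic changes should also be considered relapse". This sentence is not tied to a response category. Later in the section, such changes are only to be watched closely for emerging relapse.
- **Progressive disease.** Marrow, blood or extramedullary worsening, but only "in patients who have not previously met CR, CRi, CRc, CRm, ML-FS, or PR criteria while on study therapy".

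PR itself requires the CR blood criteria "with a decrease of at least 50% in the percentage of blasts to 5% to 24% in the bone marrow aspirate". By a second route, fewer than 5% "bone marrow blasts will be considered a PR if Auer rods are present".

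Section 9.1 ends duration of response at progression or death. Section 9.4.2 censors patients without either at the last date known alive and free of progression, and gives quartiles and a Kaplan-Meier plot once there are at least 3 responses. Duration of remission, in Section 12.1, runs to relapse and covers CR, CRi, CRc and CRm only.

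**The concern.** A duration endpoint needs an ending event for every category that can start the clock. ML-FS starts it, but no written blast level or extramedullary finding stops it. PR starts it too, but for patients with low entry blasts the stopping level lies above where they began.

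Stable disease in Section 12.1 is the residual class for anyone who meets no response, relapse or progression definition. Read literally, an ML-FS responder now at 40% marrow blasts would be called stable at that visit.

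What is at stake is duration of response. An affected patient's time runs on past regrowth to a later death or censoring date. Few responses may be available: if there were exactly three, one such patient would be a third of the data.

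**Working it through.** The plan states no figure to reproduce. The check is of the rules against each other.

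**ML-FS**

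| Rule in Section 12.1 | Does it reach an ML-FS responder? |
|---|---|
| Relapse after CR | Not named; ML-FS is defined separately from CR |
| Relapse from PR | No |
| Progressive disease (marrow, blood, extramedullary) | Expressly excluded |
| New dysplastic changes | Possibly, but the two sentences conflict |
| Duration of remission, ending at relapse | ML-FS not listed |

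A rise from under 5% to 40%, or to any other level, meets no blast-based rule.

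**PR**

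Let b be entry marrow blasts in percent.

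1. A fall of at least 50% that ends at 5% or more needs b/2 ≥ 5, so b ≥ 10.
2. Relapse from PR needs blasts ≥ 25.
3. A patient can therefore be back at b without a blast-based relapse when 10 ≤ b < 25.

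| Entry b | Highest nadir giving PR (b/2, capped at 24) | 25/b | Return to entry is relapse? |
|---|---|---|---|
| 10 | 5 | 2.50 | No |
| 15 | 7.5 | 1.67 | No |
| 20 | 10 | 1.25 | No |
| 24 | 12 | 1.04 | No |
| 25 | 12.5 | 1.00 | Yes |
| 40 | 20 | 0.62 | Yes, and already below entry |

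Two illustrations:

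- Entry 22%, PR at 10%, then 24%: 24/10 = 2.4, a rise of 140% from nadir, and above entry. Not a relapse.
- Entry 12%, PR at 6%, then 24%: 24/6 = 4 times nadir and 24/12 = 2 times entry. Not a relapse.

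The Auer-rod route to PR has the same gap at entry levels below 25%. Section 3.1.1 admits relapsed or refractory AML and higher-risk MDS and states no minimum marrow blast percentage, so such patients can enrol.

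**Link to the endpoint**

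Sections 9.1 and 9.4.2 refer to progression, which Section 12.1 makes impossible in a responder.

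- If relapse is meant to count as progression, the gaps above remain for ML-FS and for low-entry PR.
- If the words are taken literally, relapse ends no one's duration of response, and mending Section 12.1 alone would change no reported duration.

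Under either reading, duration runs past regrowth in these patients.

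**The case against.** The strongest reply concerns PR. The 25% threshold is coherent: PR ends at 24% and relapse from PR starts at 25%, so relapse means leaving the PR range. The progression rule likewise discounts change at low levels. It requires a 50% rise compared against a minimum of 20%, so a non-responder needs about 20 × 1.5 = 30% marrow blasts. Both PR illustrations end at 24% and would not be marrow progression in a non-responder either. This stands in part: the exact PR threshold is a choice, and an entry-level rule is stricter than the plan's treatment of non-responders. It does not explain a response that continues at twice the entry blast level, and it does nothing for ML-FS.

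The affected groups may be small. PR also needs the CR blood criteria. An ML-FS patient with residual cytopenia who meets the other CR criteria, including transfusion independence, also qualifies as CRi. The cited MDS criteria may contain a relapse rule for some of the 10% to under 25% group. These points limit the size, but the protocol does not say which text governs where its own definitions differ or are silent.

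Four stronger readings are tempting and are not supported:

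- That only death can end an ML-FS response. The new-dysplasia sentence is a further trigger, although it is not blast-based and its status is unclear.
- That PR durations in general are overstated by the fixed threshold. At entry levels of 25% or more, return to entry is already a relapse.
- That CRi, CRc and CRm also lack a rule. The duration-of-remission sentence already treats relapse as applying to them.
- That the 5% marrow limit should be written in for CRc and CRm. Their definitions state no marrow blast limit, so this could make a patient a relapse on the day of response.

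**Conclusion.** The point holds. Section 12.1 gives ML-FS no blast-based or extramedullary loss-of-response rule. Its PR rule lets patients entering with 10% to under 25% marrow blasts return to or exceed entry without a blast-based relapse, with the threshold at 2.5 times entry at 10% and 1.25 times at 20%. Followed exactly, the plan overstates duration of response for these patients.

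The documents do not give the share of such patients, so the effect on the quartiles cannot be estimated. One third of the data is a worst case that needs exactly three responses with one affected. The endpoint is secondary and the analysis descriptive. The RP2D, best response and response rate do not depend on it. The change should be made, but the trial's main conclusion does not rest on it.

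**What to change.** For the endpoint analysis only:

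1. In Section 12.1, state that the CR relapse rule (blood blasts reappearing, or at least 5% marrow blasts, with the existing regeneration exception) and new extramedullary disease also end response for ML-FS.
2. In Sections 9.1 and 9.4.2, name relapse alongside progression and death as the duration-of-response event and in the censoring rule. Without this, item 1 has no effect on the reported durations.
3. For PR with entry marrow blasts below 25%, count a return to the patient's own pre-treatment percentage as loss of response, keeping the regeneration and growth-factor exceptions, or at least report this as a sensitivity analysis. Say which cited criteria govern MDS.
4. Reconcile the two sentences on new dysplastic changes.

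Leave CRi, CRc and CRm as they are.

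The cost is a few lines of text and slightly shorter reported durations. On treatment, the change uses the disease assessments already scheduled every two cycles. After treatment, it relies on the clinical status reports in Section 6.8. It does not alter any rule for stopping treatment.

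### Section 12.1 gives two inconsistent rules for new dysplasia in a responder and no rule for extramedullary recurrence after response, so the end events for duration of remission and duration of response are not properly defined

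*Combined protocol and SAP*

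**What the plan says.** All of the response definitions are in Section 12.1 of the combined protocol and SAP.

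- **Relapse.** The text begins "Relapse after CR is defined as reappearance of leukemic blasts in the" peripheral blood, or at least 5% "blasts in the bone marrow not attributable to any other cause". Relapse from PR needs at least 25% marrow blasts, again excluding marrow regeneration or growth-factor effect. The entry closes with "The appearance of new dysplastic changes should also be considered relapse", and no exclusion is attached to that sentence.
- **Text after Progressive Disease.** "Appearance of new dysplastic changes should be closely monitored for emerging relapse". The reason given is that in a recently treated patient "dysplasia or a transient increase in blasts may reflect a chemotherapy effect and recovery of hematopoiesis". It continues: "Cytogenetics should be tested to distinguish true relapse from therapy-related MDS/AML".
- **Progressive Disease.** One criterion is "Development of new extramedullary disease". The category is restricted to patients who have not met any response criterion (CR, CRi, CRc, CRm, ML-FS or PR) on study therapy.
- **CR.** Extramedullary leukemia must be absent.
- **Duration of remission.** It applies to CR, CRi, CRc and CRm, and runs to the date of relapse.

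Section 9.1 ends duration of response at progression or death. Section 9.4.2 censors patients with neither event at the last date known alive and progression-free. It plans quartiles and a Kaplan-Meier plot if there are at least 3 responses. Section 9.3.3 lists morphologic relapse and progression as separate outcomes.

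**The concern.** A duration endpoint needs an end event that two readers would date the same way. Here a CR patient with marrow blasts below 5% and newly seen dysplasia has relapsed under one sentence and is still in remission, under observation, under another. No rule of precedence is given.

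The opposite error arises outside the marrow. CR requires that extramedullary disease be absent, yet its isolated return after CR or PR triggers no defined event.

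The first problem can end a duration on what may be a treatment effect; the second lets a duration run through a genuine recurrence. Both fall on responders, the only patients who contribute to these endpoints. If the text is left as it stands, the choice will be made patient by patient with outcomes already known.

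**Working it through.** The plan gives no figure to reproduce. The check applies the written definitions to each way a responder can lose response or leave follow-up. The two right-hand columns cover the two possible meanings of progression in Section 9.1.

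| Event in a responder | Duration of remission (12.1) | Duration of response, if progression includes relapse | Duration of response, if progression means Progressive Disease as in 12.1 |
|---|---|---|---|
| New dysplasia only | Ends under one sentence, continues under the other | Same conflict | Continues |
| Isolated extramedullary recurrence | Continues | Continues | Continues |
| Marrow blasts of at least 5% after CR, no other cause | Ends | Ends | Continues |
| Death | Not named as an end | Ends | Ends |

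**Row 1.** The blast criteria exclude other causes; the dysplasia sentence does not. The later paragraph supplies such an exclusion and calls for cytogenetics, but is not tied back to the relapse entry.

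**Row 2.** Relapse lists blood blasts, marrow blasts and new dysplasia. Progressive Disease lists extramedullary disease but excludes prior responders. The event therefore has no category of its own. SD is the residual class, so that assessment could be coded SD by default.

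**Row 3.** In the last column even an ordinary marrow relapse does not end the duration of response. No responder can enter Progressive Disease, so only death counts, and a living relapsed patient is censored. Section 9.3.3 separates relapse from progression, so this reading cannot be dismissed.

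**Who is affected.** Duration of remission covers CR, CRi, CRc and CRm only. Section 9.3.3 also counts ML-FS and PR as responders; for them the issue arises only through duration of response. Response rates use best response and do not change.

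**Sensitivity at the smallest planned summary.** Take 3 responders with event times t1 < t2 < t3 and assume the middle column applies. The Kaplan-Meier estimate falls to 2/3, then 1/3, then 0. The first quartile (estimate at or below 0.75) is t1, the median (at or below 0.50) is t2, and the third quartile (at or below 0.25) is t3. Each is fixed by one patient.

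Now let the middle patient's event be new dysplasia, and suppose that under the monitoring rule the patient is censored at that visit. The estimate is 2/3 after t1, stays there past t2, and is 2/3 × (1 − 1/1) = 0 after t3. The median moves from t2 to t3. If instead the first patient is reclassified, the estimate after t2 is 1 − 1/2 = 1/2 and the first quartile moves from t1 to t2. This is the extreme case, where one patient is 1/3 of the responders; the effect shrinks as responses increase.

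**The case against.** The strongest reply is that the later paragraph qualifies the earlier sentence: in a recently treated patient, look for a treatment effect before calling relapse. That is a plausible intention, and monitoring with cytogenetics is more than watching. But the relapse sentence is unqualified and nothing says which text governs. Section 12.1 also cites published AML and MDS response criteria. Those sources are not available here, and the protocol does not say that they override its own definitions.

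Several stronger readings are tempting but unsupported:

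- *Duration of response certainly ends on the wrong events because relapse is misdefined.* Section 9.1 does not name relapse. The dysplasia and extramedullary errors in the relapse definition reach duration of response only if progression includes relapse. Otherwise the fault is different: only death ends it.
- *Calling relapse on dysplasia moves the date by at least 2 × 21 = 42 days, the gap between scheduled assessments.* This is not a lower bound. Blood blasts alone establish relapse after CR, the calendar has a CBC with differential on Day 1 of every 21-day cycle, and Section 12 allows extra marrow procedures after CR. After treatment stops, follow-up under Section 6.8 is about every 2 months.
- *The CR entry, "Persistent dysplasia is allowed", contradicts the relapse sentence, so MDS patients with background dysplasia would be called relapsed.* That entry concerns persistent dysplasia; the relapse sentence concerns new changes.

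It also stands that the endpoints are secondary and, under Section 9.4, descriptive. With few responses the planned summary may not be produced at all.

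**Conclusion.** The concern holds on two textual points: Section 12.1 has two unreconciled rules for new dysplasia in a responder, and isolated extramedullary recurrence after CR or PR is neither relapse nor progression. Duration of remission is affected directly. Duration of response is misdefined under either meaning of progression, though in different ways.

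The size is limited. Dose-limiting toxicity, the RP2D, the sample size and the response rate are unaffected. What can change is the dating or counting of individual end events among few responders, where one patient can move a quartile. How often this would happen cannot be estimated, because the documents give no expected frequency of new dysplasia or extramedullary recurrence. The conclusion assumes that the definitions written in Section 12.1 are the ones applied.

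**What to change.** Three edits, to be made before responder durations are analysed:

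1. In Section 12.1, reconcile the two dysplasia sentences into a single rule that applies the treatment-effect qualification consistently, and say what date a relapse confirmed under it carries.
2. Add new or recurrent extramedullary disease to the definitions of relapse after CR and relapse from PR.
3. In Sections 9.1 and 9.4.2, state that relapse after response, as defined in Section 12.1, is an end event for duration of response alongside progression and death, and make the censoring rule match.

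No molecular relapse criterion should be added as part of this. None of the current relapse definitions contains one, and the calendar names NPM1, FLT3 and CEBPA only at baseline, so it would be a new criterion needing its own assessment schedule.

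The cost is a few sentences and no new procedure: cytogenetic testing is already called for, and the absence of extramedullary disease is already part of CR. The downside is that a few event dates may change, making some durations slightly shorter or longer.
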